6. STUDY OVERVIEW

This is a Phase 2, randomized, single-blind, active-controlled dose-ranging study in patients scheduled to undergo total knee arthroplasty (TKA). Approximately 60 subjects (15 per treatment group) are planned for enrollment. Subjects will be randomized in a 1:1:1:1 ratio to receive DepoTXA 400 mg, DepoTXA 800 mg, DepoTXA 1200 mg, or IV TXA (Cyklokapron® 1 gram).

Blood samples for PK analysis will be obtained at baseline (prior to study drug administration); at 5, 15, and 30 minutes; and at 1, 2, 4, 6, 8, 12, 16, and 24 hours after study drug administration for all treatment groups. Additional blood samples will be collected at 36, 48, 60, 72, and 96 hours after study drug administration for DepoTXA-treated subjects.

Postsurgical efficacy assessments will include measurement of blood loss (as assessed by hemoglobin [Hb] and hematocrit [Hct] levels), transfusion requirement, knee flexion, timed up-and-go (TUG) test, knee and thigh measurements, numeric rating scale (NRS_ pain scores), days to independent ambulation, and the surgical wound aspect score (SWAS).

Postsurgical safety assessments will include vital signs, neurological assessment, clinical laboratory testing (hematology, chemistry, and coagulation), 12-lead electrocardiogram (ECG), and adverse event (AE) monitoring. Subject monitoring will include, but not be limited to, changes in vision, neurologic function, or renal function; and occurrence of hematoma, wound dehiscence/disruption, surgical site infection (per Centers for Disease Control and Prevention definition), nausea, vomiting, and diarrhea.

Adverse events of special interest (AESI) include changes in color vision, venous thromboembolism or pulmonary embolism, and oliguria. If an AESI or serious AE (SAE) occurs during the study, an unscheduled PK blood sample must be collected. In addition, vital signs, the neurological assessment, and clinical laboratory tests must be conducted, as appropriate. If a subject experiences changes in color vision, an ophthalmological consultation must be ordered.

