9.9. Safety Analyses

The following safety assessments will be summarized:

- 12-lead ECGs at day 1 Preop (D1 Preop), and 1 hour and 12 hours after study drug administration.
- Vital signs (resting heart rate and blood pressure) at Baseline, and 5min, 15min, 30min, 1hr, 2hr, 4hr, 6hr, 8hr, 12hr, 16hr, 24hr, 36hr, 48hr, 60hr, 72hr, and 96hr after study drug administration.
- Neurological assessment at D1 Preop and at 12, 24, 36, 48, 60, 72, and 96 hours after study drug administration.
- Clinical laboratory testing (hematology [including fibrinogen and fibrin split products, lipid profile] and chemistry) at D1 Preop, at 48 hours, and at day 7.
- Creatinine clearance measurement at 48 hours and at day 7.
- Reoperations due to hematoma or wound dehiscence.
- Adverse events through study day 60.

No inferential statistics are planned for any of the safety assessments.

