9.9.3. Neurological Assessments

The neurological assessments summary will include the proportion of subjects who are oriented, and proportion of subjects who have any of the neurologic events (answered “Yes” to any of the additional questions regarding numbness, taste, hearing, vision, or twitching). Percentages will be based on the number of subjects in the treatment group. The number and percentage of subjects will be tabulated by treatment group at each assessment timepoint.

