		SD	x.xx	x.xx	x.xx				
		Minimum	xx	xx	xx				
		Median	xx.x	xx.x	xx.x				
		Maximum	xx	xx	xx				
Change from Baseline	Actual	n	xx	xx	xx				
		Mean	xx.x	xx.x	xx.x				
		SD	x.xx	x.xx	x.xx				
		Minimum	xx	xx	xx				
		Median	xx.x	xx.x	xx.x				
		Maximum	xx	xx	xx				

Source: list SAS datasets used to create table
SAS X.Y

DDMONYYYYTHH:MM
program_name

Note to programmer: Only present overall sites. Vital signs are 'Resting Heart Rate (bpm)', 'Systolic Blood Pressure (mmHg)' and 'Diastolic Blood Pressure (mmHg)'. Timepoints to appear on this table are Baseline, 5min, 15min, 30min, 1hr, 2hr, 4hr, 6hr, 8hr, 12hr, 16hr, 24hr, 36hr, 48hr, 60hr, 72hr, and 96hr. Don't split timepoints across pages. See SAP section 9.9.2 for further details.

Pacira Pharmaceuticals		(Page X of Y)		Protocol: 404-C-201					
Table 14.3-3: Tabulation of Neurological Assessments by Timepoint- Safety Analysis Set									
Site: Overall									
Timepoint: Baseline									
Assessment	Score	DepoTXA 400 [N=XX] n (%)	DepoTXA 800 [N=XX] n (%)	DepoTXA 1200 [N=XX] n (%)	IV TXA [N=XX] n (%)				
Subject Oriented		xx (xx.x)	xx (xx.x)	xx (xx.x)	xx (xx.x)				
		xx (xx.x)	xx (xx.x)	xx (xx.x)	xx (xx.x)				
Numbness		xx (xx.x)	xx (xx.x)	xx (xx.x)	xx (xx.x)				
		xx (xx.x)	xx (xx.x)	xx (xx.x)	xx (xx.x)				
Metallic taste		xx (xx.x)	xx (xx.x)	xx (xx.x)	xx (xx.x)				
		xx (xx.x)	xx (xx.x)	xx (xx.x)	xx (xx.x)				
Hearing problems		xx (xx.x)	xx (xx.x)	xx (xx.x)	xx (xx.x)				
		xx (xx.x)	xx (xx.x)	xx (xx.x)	xx (xx.x)				
Vision problems		xx (xx.x)	xx (xx.x)	xx (xx.x)	xx (xx.x)				
		xx (xx.x)	xx (xx.x)	xx (xx.x)	xx (xx.x)				
Muscle twitching		xx (xx.x)	xx (xx.x)	xx (xx.x)	xx (xx.x)				
		xx (xx.x)	xx (xx.x)	xx (xx.x)	xx (xx.x)				

Note: Numbness refers to the numbness of the lips, tongue, and/or mouth.

Source: list SAS datasets used to create table
SAS X.Y

DDMONYYYYTHH:MM
program_name

Note to programmer: Only present overall sites. Timepoints to appear on this table are, in order of appearance, Baseline (prior to surgery), At anytime after baseline, 12, 24, 36, 48, 60, 72, 84 and 96 hours. Do not split a timepoint across pages. For the timepoint 'anytime after baseline' if there is at least one 'yes' at any timepoint but baseline, the subject will be a 'yes'.

Pacira Pharmaceuticals		(Page X of Y)		Protocol: 404-C-201					
Table 14.3-4.1: Summary of Clinical Laboratory Assessments - Safety Analysis Set									
Site: Overall									
Clinical Laboratory Parameter: Albumin (g/L)									

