		48h	DDMONYYYYTHH:MM	XX.X	XX.X	XX.X	XX.X	Left TKA
		Day7	DDMONYYYYTHH:MM	XX.X	XX.X	XX.X	XX.X	Left TKA
XXX	XXX-YYYY	D1 Preop	DDMONYYYYTHH:MM	XX.X	XX.X	XX.X	XX.X	Right TKA
		48h	DDMONYYYYTHH:MM	XX.X	XX.X	XX.X	XX.X	Right TKA
		Day7	DDMONYYYYTHH:MM	XX.X	XX.X	XX.X	XX.X	Right TKA

ND=Not Done, NA=Not Applicable

* = out of window

Source: list SAS datasets used to create listing
SAS X.Y

DDMONYYYYTHH:MM
program_name

Pacira Pharmaceuticals
Listing 16.2-6.7: Surgical Wound Aspect Score (SWAS) - Randomized Subjects
TREATMENT: *treatment-name*

Site	Subject	Timepoint	Date Time	Numerical Score			
				Wound	Oozing	Erythema	Ecchymosis
XXX	XXX-YYYY	D1 Preop	DDMONYYYYTHH:MM	x		x	x
		48h	DDMONYYYYTHH:MM	x		x	x
		Day7	DDMONYYYYTHH:MM	x		x	x
XXX	XXX-YYYY	D1 Preop	DDMONYYYYTHH:MM	x		x	x
		48h	DDMONYYYYTHH:MM	x		x	x
		Day7	DDMONYYYYTHH:MM	x		x	x
XXX	XXX-YYYY	D1 Preop	DDMONYYYYTHH:MM	x		x	x
		48h	DDMONYYYYTHH:MM	x		x	x
		Day7	DDMONYYYYTHH:MM	x		x	x

ND=Not Done, NA=Not Applicable,

* = out of window

Source: list SAS datasets used to create listing
SAS X.Y

DDMONYYYYTHH:MM
program_name

Pacira Pharmaceuticals
Listing 16.2-7: Phone Calls - Randomized Subjects

Protocol: 404-C-201

Treatment: TTTTTT

Site	Subject	Date of Phone Contact	Scheduled Timepoint	Was the Call Made?	Was there a reoperation?	Number of Reoperations	Independent Ambulation?	Date of Ind. Amb.
XXX	XXX-YYYY	DDMONYYYY	Day 14	Y	N	NA	N	NA
	XXX-YYYY	DDMONYYYY	Day 30	Y	N	NA	Y	DDMONYYYY
	XXX-YYYY	DDMONYYYY	Day 60	Y	N	NA	Y	DDMONYYYY
XXX	XXX-YYYY	DDMONYYYY	Day 14	N	ND	NA	ND	NA
	XXX-YYYY	DDMONYYYY	Day 30	Y	N	NA	N	NA
	XXX-YYYY	DDMONYYYY	Day 60	Y	N	NA	Y	DDMONYYYY
XXX	XXX-YYYY	DDMONYYYY	Day 14	Y	N	NA	N	NA
	XXX-YYYY	DDMONYYYY	Day 30	Y	N	NA	N	NA
	XXX-YYYY	DDMONYYYY	Day 60	Y	Y	x	N	NA

ND=Not Done, NA=Not Applicable

Source: list SAS datasets used to create listing
SAS X.Y

DDMONYYYYTHH:MM
program_name

Pacira Pharmaceuticals
Listing 16.2-8: Neurological Assessment - Randomized Subjects

Protocol: 404-C-201

Treatment: TTTTTTT

Site	Subject	Date and Time Of Assessment	Time From Dose			Questions					
			Scheduled (hr)	Actual (hr)	Deviation (mins)	1	2	3	4	5	6
XXX	XXX-YYYY	DDMONYYYYTHH:MM	Screening	NA	NA	XXX	XXX	XXX	XXX	XXX	XXX
		DDMONYYYYTHH:MM	D1 PREOP	NA	NA	XXX	XXX	XXX	XXX	XXX	XXX
		DDMONYYYYTHH:MM	12	0.XX	X	XXX	XXX	XXX	XXX	XXX	XXX
		DDMONYYYYTHH:MM	24	X	X	XXX	XXX	XXX	XXX	XXX	XXX
		DDMONYYYYTHH:MM	36	ND							
		DDMONYYYYTHH:MM	48	X	X	XXX	XXX	XXX	XXX	XXX	XXX
		DDMONYYYYTHH:MM	60	X	X	XXX	XXX	XXX	XXX	XXX	XXX

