		DDMONYYYYTHH:MM	72	XX	X	XXX	XXX	XXX	XXX	XXX	XXX
		DDMONYYYYTHH:MM	96	XX	X	XXX	XXX	XXX	XXX	XXX	XXX
		DDMONYYYYTHH:MM	Screening	NA	NA	XXX	XXX	XXX	XXX	XXX	XXX
XXX-YYYY	XXX-YYYY	DDMONYYYYTHH:MM	D1 PREOP	NA	NA	XXX	XXX	XXX	XXX	XXX	XXX
		DDMONYYYYTHH:MM	12	XX	X	XXX	XXX	XXX	XXX	XXX	XXX
		DDMONYYYYTHH:MM	24	XX	X	XXX	XXX	XXX	XXX	XXX	XXX
		DDMONYYYYTHH:MM	36	XX	-X	XXX	XXX	XXX	XXX	XXX	XXX
		DDMONYYYYTHH:MM	48	XX	X	XXX	XXX	XXX	XXX	XXX	XXX
		DDMONYYYYTHH:MM	60	XX	X	XXX	XXX	XXX	XXX	XXX	XXX
		DDMONYYYYTHH:MM	72	XX	X	XXX	XXX	XXX	XXX	XXX	XXX
		DDMONYYYYTHH:MM	96	XX	X	XXX	XXX	XXX	XXX	XXX	XXX

- 1) Is subject oriented?
- 2) Do you have numbness of the lips, the tongue or around the mouth?
- 3) Do you have a metallic taste in your mouth?
- 4) Are you having problems with your hearing not related to the use of a hearing aid?
- 5) Are you having problems with your vision no related to the use of eye glasses?
- 6) Are your muscles twitching?

Source: list SAS datasets used to create listing
SAS X.Y

DDMONYYYYTHH:MM
program_name

Pacira Pharmaceuticals
(Page X of Y)
Listing 16.2-9: Electrocardiogram Findings - Investigator Assessment - All Subjects
Treatment: DepoTXA 400

Protocol: 404-C-201

Site	Subject	Date and Time of Sample	Time From Dose				If "Abnormal", specify
			Scheduled Timepoint	Actual (hr)	Deviation (mins)	Finding	
XXX	XXX-YYYY	DDMONYYYYTHH:MM	D1PreOp	NA	NA	Normal	
		DDMONYYYYTHH:MM	1h	XX.X	X	Normal	
		DDMONYYYYTHH:MM	12h	XX.X	X	Normal	
	XXX-YYYY	DDMONYYYYTHH:MM	D1PreOp	NA	NA	Normal	
		DDMONYYYYTHH:MM	1h	XX.X	X	Normal	
		DDMONYYYYTHH:MM	12h	XX.X	X	Normal	
	XXX-YYYY	DDMONYYYYTHH:MM	D1PreOp	NA	NA	Normal	
		DDMONYYYYTHH:MM	1h	XX.X	X	Normal	
		DDMONYYYYTHH:MM	12h	XX.X	X	Normal	

NA=Not applicable

ND=Not done

Source: list SAS datasets used to create listing
SAS X.Y

DDMONYYYYTHH:MM
program_name

Pacira Pharmaceuticals
Listing 16.2-10: Vital Signs - All Subjects
Treatment: TTTTTTT
SITE: XXX

(Page X of Y)

Protocol: 404-C-201

Subject	Visit	Date and Time	Time from Dose			Heart Rate (bpm)	Blood Pressure		Body Mass		
			Sched (hr)	Actual (hr)	Deviation (mins)		Sys. (mmHg)	Dia. (mmHg)	Height (cm)	Weight (kg)	Index (m/kg ²)
XXX-YYYY	Screening	DDMONYYYYTHH:MM	NA	NA	NA	XX	XXX	XXX	XXX	XXX	XXX
	D1 Preop	DDMONYYYYTHH:MM	0	X	X	XX	XXX	XXX			
	5 min	DDMONYYYYTHH:MM	0.08	X	X	XX	XXX	XXX			
	15 min	DDMONYYYYTHH:MM	0.25	X	X	XX	XXX	XXX			
	30 min	DDMONYYYYTHH:MM	0.50	X	-X	XX	XXX	XXX			
	1h	DDMONYYYYTHH:MM	1	X	X	XX	XXX	XXX			
	2h	DDMONYYYYTHH:MM	2	X	X	XX	XXX	XXX			

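### The any-'yes' roll-up in Table 14.3-3 also covers orientation, where 'yes' is the normal answer, so intermittently disoriented subjects are counted as oriented

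*SAP*

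**What the plan says.** Table 14.3-3 (SAP section 13) is a single shell with six rows. The first is "Subject Oriented"; the other five are numbness, metallic taste, hearing problems, vision problems and muscle twitching. The note under the shell asks for these pages: "Baseline (prior to surgery), At anytime after baseline, 12, 24, 36, 48, 60, 72, 84 and 96 hours". For the page covering any time after baseline it gives one rule, "if there is at least one 'yes' at any timepoint but baseline, the subject will be a 'yes", and exempts no row.

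Listing 16.2-8 (SAP section 14) gives the wording of the six questions. The first is "Is subject oriented". The other five ask whether the subject has a symptom.

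Section 9.9.3 keeps the two kinds of item apart. It reports the proportion oriented, and separately the proportion with a neurologic event, meaning a 'yes' "to any of the additional questions regarding numbness, taste, hearing, vision, or twitching". It describes tabulation by timepoint and gives no rule for combining orientation across visits.

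**The concern.** For the five symptom items, any-'yes' means the subject had the symptom at least once, which is what a safety roll-up should show. For orientation the answer scale runs the other way, so the same rule means the subject was oriented at least once. One page then mixes worst-case counts in five rows with a best-case count in the sixth, with nothing to tell the reader so.

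At stake is the number of subjects disoriented at any time after dosing. This is the only page of Table 14.3-3 that counts subjects across visits. A reader who sees zero not oriented there would naturally conclude that nobody was ever disoriented, and that could be false. Safety is a secondary objective (section 5.2), and changes in neurologic function are among the things monitored (section 6).

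**Working it through.** The plan states no figure on this point, so there is none to reproduce. The check applies the rule to the possible answers.

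**Inputs**

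- Roll-up rule: any post-baseline 'yes' gives 'yes', for every row (note to Table 14.3-3).
- Meaning of 'yes' for orientation: oriented, hence normal (Listing 16.2-8).
- Post-dose assessments: seven. Section 9.9 has "Neurological assessment at D1 Preop and at 12, 24, 36, 48, 60, 72, and 96 hours after study drug administration".
- Arm size: 15. Section 6 has "Approximately 60 subjects (15 per treatment group) are planned for enrollment".
- Denominator: the number of subjects in the treatment group (section 9.9.3).

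**Step 1: what the rule returns for orientation.** Let m be the number of 'no' answers among seven recorded assessments.

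| m | True status | Shown under the note | Shown if any 'no' gives 'no' |
|---|---|---|---|
| 0 | never disoriented | oriented | oriented |
| 1 to 6 | disoriented at some assessments | oriented | not oriented |
| 7 | disoriented at every assessment | not oriented | not oriented |

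There are 2^7 = 128 possible answer sequences, and 128 − 1 = 127 contain at least one 'no'. The note shows 126 of those 127 as oriented and 1 as not oriented. The note also lists an 84-hour time that section 9.9 does not schedule. With eight assessments there are 2^8 = 256 sequences, 255 contain a 'no', and 254 of them are shown as oriented. These are counts of patterns, not probabilities.

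**Step 2: size per subject.** Each subject with m from 1 to 6 is missing from the not-oriented count. In a 15-subject arm that is 1/15 = 6.7 percentage points.

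**Step 3: can the timepoint pages supply the count?** Suppose each of the seven timepoint pages shows exactly one not-oriented subject in a 15-subject arm, with all assessments recorded.

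- If it is the same subject each time, one subject was ever disoriented: 1/15 = 6.7%. The roll-up page shows 1.
- If it is a different subject each time, seven were: 7/15 = 46.7%. The roll-up page shows 0, because none of them has 'no' at all seven.
- For any number from 2 to 7, the roll-up page shows 0.

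The timepoint pages are therefore compatible with anything from 1 to 7 subjects, and the roll-up page gives the right number only at 1.

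**The case against.** The strongest reply is that section 9.9.3, the body text, attaches the any-'yes' idea only to the five additional questions. A programmer who reads the note alongside it might leave orientation out. That is possible, but section 9.9.3 says nothing about rolling orientation up over visits, so it does not override a note that exempts no row. Following the note to the letter gives the wrong count.

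Second, the entry is literally true if the row is read as oriented at least once. That stands as a matter of wording, but such a count has little use as a safety summary and is easily misread.

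Third, the score labels of the shell could not be read in the text available, so the yes/no display of the orientation row is inferred. The note's own use of 'yes' and the question in the listing support that inference, and the labels can be checked in the SAP itself.

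Fourth, the consequence is limited, and this stands in full. The timepoint pages are right. The listing shows every answer, so with about 60 subjects the correct count can be made by hand. Disorientation reported as an adverse event would also be counted once per subject in the treatment-emergent event tables. The page understates only if some subject is intermittently disoriented, and the SAP does not indicate how often that happens.

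**Conclusion.** The concern holds, as a minor point. As written, the note turns the orientation row of the any-time page into a best-case count and can understate how many subjects were ever disoriented after dosing. Each subject affected costs 6.7 percentage points in a planned arm of 15. How many subjects would be affected is not known, and no rate is claimed.

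The conclusion rests on two things: orientation is recorded as yes or no with 'yes' meaning oriented, and the note applies to every row because it exempts none. The exact split in the table above also assumes that all seven assessments are recorded. If some are missing, a subject is shown as not oriented only when every recorded post-baseline answer is 'no'. The summary is descriptive; no inferential safety statistics are planned, and the primary pharmacokinetic objective is unaffected.

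**What to change.** In the note to Table 14.3-3, limit the any-'yes' rule to the five symptom items. Add one sentence for orientation: on the page for any time after baseline, the subject is a 'no' if any post-baseline assessment is 'no'. A row label or footnote saying that this line counts subjects not oriented at least once would prevent misreading.

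The cost is one sentence in the programming note and one reversed condition in the program. No new data are needed, and no other page of the table changes.

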Listing 16.2-18.2: Pharmacokinetic Parameters - All Subjects	101
Listing 16.2-19: Unique Adverse Events Terms and Associated Coded Terms	102
Listing 16.2-20: Unique Medication Terms and Associated Coded Terms	103

Pacira Pharmaceuticals
Listing 16.2-1: Subject Disposition - All Subjects

(Page X of Y)

Protocol: 404-C-201

Treatment: TTTTTT

Site	Subject	Date of			Specify
		Last Visit	End of Study	Status	
XXX	XXX-YYYY	DDMONYYYY			

Source: list SAS datasets used to create listing
SAS X.Y

DDMONYYYYTHH:MM
program_name

Note to programmer: End of study status for subject who early terminated from the study is the primary reason for termination. If subject discontinued due to an AE then the reason should read 'ADVERSE EVENT, AE # X'. If subject discontinued due to death the reason should read 'DEATH ON DDMONYYYY'. For those reasons that also collected a specify text, that text belongs in the specify column. Screen Failures should be indicated under treatment at the top of the table and the reason for screen failure should be provided.

Pacira Pharmaceuticals
Listing 16.2-2: Randomization and Analysis Sets - Randomized Subjects
Treatment: TTTTTT

Protocol: 404-C-201

Site	Subject	Date and Time	Randomization Number	Analysis Sets		
				Safety	PK	Efficacy
XXX	XXX-YYYY	DDMONYYYYTHH:MM	XXXXX	XXX	XXX	XXX

Source: list SAS datasets used to create listing
SAS X.Y

DDMONYYYYTHH:MM
program_name

Pacira Pharmaceuticals
Listing 16.2-3: Demographics - All Subjects
Treatment: TTTTTT

(Page X of Y)

Protocol: 404-C-201

Site	Subject	Birth Date	Age (yrs)	ASA Class	Sex	Race	Ethnicity
XXX	XXX-YYYY	DDMONYYYY	XX	XXXXXX	XXXXXXXXXXXXXXXXXXXX	XXXXXXXXXXXXXXXXXXXX	XXXXXXXXXXXXXXXXXXXX

Source: list SAS datasets used to create listing
SAS X.Y

DDMONYYYYTHH:MM
program_name

Pacira Pharmaceuticals
Listing 16.2-4.1: Surgery Characteristics - Randomized Subjects
Treatment: TTTTTT

Site	Subject	Date	Surgery Time		Duration (hr)	Procedure Name	Incision Length (cm)	Anesthesia Type	Primary Surgeon
			Start	Stop					
XXX	XXX-YYYY	DDMONYYYY	HH:MM	HH:MM	XX.X	Right TKA	xx.x	xxxxxxxx	xxx
XXX	XXX-YYYY	DDMONYYYY	HH:MM	HH:MM	XX.X	Left TKA	xx.x	xxxxxxxx	xxx
XXX	XXX-YYYY	DDMONYYYY	HH:MM	HH:MM	XX.X	Right TKA	xx.x	xxxxxxxx	xxx
XXX	XXX-YYYY	DDMONYYYY	HH:MM	HH:MM	XX.X	Left TKA	xx.x	xxxxxxxx	xxx
XXX	XXX-YYYY	DDMONYYYY	HH:MM	HH:MM	XX.X	Right TKA	xx.x	xxxxxxxx	xxx
XXX	XXX-YYYY	DDMONYYYY	HH:MM	HH:MM	XX.X	Right TKA	xx.x	xxxxxxxx	xxx

Source: list SAS datasets used to create listing

SAS X.Y

DDMONYYYYTHH:MM

program_name

Pacira Pharmaceuticals
Listing 16.2-4.2: Tourniquet Characteristics - Randomized Subjects
Treatment: TTTTTT

(Page X of Y)

Protocol: 404-C-201

Site	Subject	Date	Tourniquet Used?	Tourniquet Time			Maximum Pressure (mmHg)
				Start	Stop	Duration (hr)	
XXX	XXX-YYYY	DDMONYYYY	xxx	HH:MM	HH:MM	XX.X	xxx
XXX	XXX-YYYY	DDMONYYYY	xxx	HH:MM	HH:MM	XX.X	xxx
XXX	XXX-YYYY	DDMONYYYY	xxx	HH:MM	HH:MM	XX.X	xxx
XXX	XXX-YYYY	DDMONYYYY	xxx	HH:MM	HH:MM	XX.X	xxx
XXX	XXX-YYYY	DDMONYYYY	xxx	HH:MM	HH:MM	XX.X	xxx
XXX	XXX-YYYY	DDMONYYYY	xxx	HH:MM	HH:MM	XX.X	xxx

Source: list SAS datasets used to create listing
SAS X.Y

DDMONYYYYTHH:MM
program_name

Pacira Pharmaceuticals (Page X of Y)
Listing 16.2-5: Study Drug Administration - Randomized Subjects

Protocol: 404-C-201

Site	Subject	Study Treatment			Date	Start Time	Stop Time	Total Volume (mL)
		Randomized	Actual					
XXX	XXX-YYYY	XXXXXXXXXXXXXX	XXXXXXXXXXXXXX		DDMONYYYY	HH:MM	HH:MM	X
XXX	XXX-YYYY	XXXXXXXXXXXXXX	XXXXXXXXXXXXXX		DDMONYYYY	HH:MM	HH:MM	X
XXX	XXX-YYYY	XXXXXXXXXXXXXX	XXXXXXXXXXXXXX		DDMONYYYY	HH:MM	HH:MM	X
XXX	XXX-YYYY	XXXXXXXXXXXXXX	XXXXXXXXXXXXXX		DDMONYYYY	HH:MM	HH:MM	X
XXX	XXX-YYYY	XXXXXXXXXXXXXX	XXXXXXXXXXXXXX		DDMONYYYY	HH:MM	HH:MM	X
XXX	XXX-YYYY	XXXXXXXXXXXXXX	XXXXXXXXXXXXXX		DDMONYYYY	HH:MM	HH:MM	X

Source: list SAS datasets used to create listing
SAS X.Y

DDMONYYYYTHH:MM
program_name

Pacira Pharmaceuticals
Listing 16.2-6.1.1: Calculated Blood Loss - Method 1 - Randomized Subjects
Randomized Treatment: TTTTTT

(Page X of Y)

Protocol: 404-C-201

Site	Subject	Date and Time	Timepoint	Blood Volume Transfused (mL)	Hematocrit (%)	Calculated Blood Volume (mL)	Calculated Blood Loss (mL)
XXX	XXX-YYYY	DDMONYYYYTHH:MM	Baseline	xxx.x	xxx.x	xxxx.x	N/A
		DDMONYYYYTHH:MM	PACU	xxx.x	xxx.x	xxxx.x	xxx.x
		DDMONYYYYTHH:MM	6 hrs	xxx.x	xxx.x	xxxx.x	xxx.x
		DDMONYYYYTHH:MM	12 hrs	xxx.x	xxx.x	xxxx.x	xxx.x
		DDMONYYYYTHH:MM	24 hrs	xxx.x	xxx.x	xxxx.x	xxx.x
		DDMONYYYYTHH:MM	48 hrs	xxx.x	xxx.x	xxxx.x	xxx.x
		DDMONYYYYTHH:MM	72 hrs	xxx.x	xxx.x	xxxx.x	xxx.x
		DDMONYYYYTHH:MM	120 hrs	xxx.x	xxx.x	xxxx.x	xxx.x
		DDMONYYYYTHH:MM	Day 7	xxx.x	xxx.x	xxxx.x	xxx.x
		DDMONYYYYTHH:MM	Baseline	xxx.x	xxx.x	xxxx.x	N/A
XXX	XXX-YYYY	DDMONYYYYTHH:MM	PACU	xxx.x	xxx.x	xxxx.x	xxx.x
		DDMONYYYYTHH:MM	6 hrs	xxx.x	xxx.x	xxxx.x	xxx.x
		DDMONYYYYTHH:MM	12 hrs	xxx.x	xxx.x	xxxx.x	xxx.x
		DDMONYYYYTHH:MM	24 hrs	xxx.x	xxx.x	xxxx.x	xxx.x
		DDMONYYYYTHH:MM	48 hrs	xxx.x	xxx.x	xxxx.x	xxx.x
		DDMONYYYYTHH:MM	72 hrs	xxx.x	xxx.x	xxxx.x	xxx.x
		DDMONYYYYTHH:MM	120 hrs	xxx.x	xxx.x	xxxx.x	xxx.x
		DDMONYYYYTHH:MM	Day 7	xxx.x	xxx.x	xxxx.x	xxx.x

Note: Blood volume transfused is since the last Timepoint. Blood Volume is calculated according to section 9.8.1 of the Statistical Analysis Plan for study 404-C-201: For method 1, blood loss is in mL calculated by: $RBC_{lost} = BV_{baseline} * (Hct_{baseline} - Hct_{post-op\ hour}) + BV_{transfused}$

Source: list SAS datasets used to create listing
SAS X.Y

DDMONYYYYTHH:MM
program_name

Note to programmer: Sort by collection date and time. Timepoints outside of the schedule windows should be listed under "Scheduled Timepoint" as "Unscheduled". Do not split a subject's data across pages.

Pacira Pharmaceuticals
Listing 16.2-6.1.2: Calculated Blood Loss - Method 2 - Randomized Subjects
Randomized Treatment: TTTTTT

(Page X of Y)

Protocol: 404-C-201

Site	Subject	Date and Time	Timepoint	Blood Volume Transfused (g)	Hemoglobin (g/dL)	Calculated Blood Volume (mL)	Calculated Blood Loss (mL)
XXX	XXX-YYYY	DDMONYYYYTHH:MM	Baseline	xxx.x	xxx.x	xxxx.x	N/A
		DDMONYYYYTHH:MM	PACU	xxx.x	xxx.x	xxxx.x	xxx.x
		DDMONYYYYTHH:MM	6 hrs	xxx.x	xxx.x	xxxx.x	xxx.x
		DDMONYYYYTHH:MM	12 hrs	xxx.x	xxx.x	xxxx.x	xxx.x
		DDMONYYYYTHH:MM	24 hrs	xxx.x	xxx.x	xxxx.x	xxx.x
		DDMONYYYYTHH:MM	48 hrs	xxx.x	xxx.x	xxxx.x	xxx.x
		DDMONYYYYTHH:MM	72 hrs	xxx.x	xxx.x	xxxx.x	xxx.x
		DDMONYYYYTHH:MM	120 hrs	xxx.x	xxx.x	xxxx.x	xxx.x
		DDMONYYYYTHH:MM	Day 7	xxx.x	xxx.x	xxxx.x	xxx.x
		DDMONYYYYTHH:MM	Baseline	xxx.x	xxx.x	xxxx.x	N/A
XXX	XXX-YYYY	DDMONYYYYTHH:MM	PACU	xxx.x	xxx.x	xxxx.x	xxx.x
		DDMONYYYYTHH:MM	6 hrs	xxx.x	xxx.x	xxxx.x	xxx.x
		DDMONYYYYTHH:MM	12 hrs	xxx.x	xxx.x	xxxx.x	xxx.x
		DDMONYYYYTHH:MM	24 hrs	xxx.x	xxx.x	xxxx.x	xxx.x
		DDMONYYYYTHH:MM	48 hrs	xxx.x	xxx.x	xxxx.x	xxx.x
		DDMONYYYYTHH:MM	72 hrs	xxx.x	xxx.x	xxxx.x	xxx.x
		DDMONYYYYTHH:MM	120 hrs	xxx.x	xxx.x	xxxx.x	xxx.x
		DDMONYYYYTHH:MM	Day 7	xxx.x	xxx.x	xxxx.x	xxx.x

Blood volume transfused is since the last Timepoint. Blood Volume is calculated according to section 9.8.1 of the Statistical Analysis Plan for study 404-C-201: For method 2, blood loss is in mL calculated by:

$$RBC_{lost} = \frac{1000 * (BV_{baseline} * (Hb_{baseline} - Hb_{post-op\ hour})) * 0.001 + 52 * BV_{transfused}}{Hb_{baseline}}$$

Source: list SAS datasets used to create listing
SAS X.Y

DDMONYYYYTHH:MM
program_name

Note to programmer: Sort by collection date and time. Timepoints outside of the schedule windows should be listed under "Scheduled Timepoint" as "Unscheduled". Do not split a subject's data across pages.

Pacira Pharmaceuticals
(Page X of Y)
Listing 16.2-6.2: Blood Transfusion - Randomized Subjects

Protocol: 404-C-201

Treatment: TTTTTT

Site	Subject	Start Date and Time	End Date and Time	# of Units	Associated Adverse Event
XXX	XXX-YYYY	DDMONYYYYTHH:MM	DDMONYYYYTHH:MM	×	Preferred Term
	XXX-YYYY	DDMONYYYYTHH:MM	DDMONYYYYTHH:MM	×	Preferred Term
	XXX-YYYY	DDMONYYYYTHH:MM	DDMONYYYYTHH:MM	×	Preferred Term
	XXX-YYYY	DDMONYYYYTHH:MM	DDMONYYYYTHH:MM	×	Preferred Term
	XXX-YYYY	DDMONYYYYTHH:MM	DDMONYYYYTHH:MM	×	Preferred Term
	XXX-YYYY	DDMONYYYYTHH:MM	DDMONYYYYTHH:MM	×	Preferred Term
	XXX-YYYY	DDMONYYYYTHH:MM	DDMONYYYYTHH:MM	×	Preferred Term
	XXX-YYYY	DDMONYYYYTHH:MM	DDMONYYYYTHH:MM	×	Preferred Term
	XXX-YYYY	DDMONYYYYTHH:MM	DDMONYYYYTHH:MM	×	Preferred Term
XXX	XXX-YYYY	DDMONYYYYTHH:MM	DDMONYYYYTHH:MM	×	Preferred Term
	XXX-YYYY	DDMONYYYYTHH:MM	DDMONYYYYTHH:MM	×	Preferred Term
	XXX-YYYY	DDMONYYYYTHH:MM	DDMONYYYYTHH:MM	×	Preferred Term
	XXX-YYYY	DDMONYYYYTHH:MM	DDMONYYYYTHH:MM	×	Preferred Term
	XXX-YYYY	DDMONYYYYTHH:MM	DDMONYYYYTHH:MM	×	Preferred Term
	XXX-YYYY	DDMONYYYYTHH:MM	DDMONYYYYTHH:MM	×	Preferred Term
	XXX-YYYY	DDMONYYYYTHH:MM	DDMONYYYYTHH:MM	×	Preferred Term
	XXX-YYYY	DDMONYYYYTHH:MM	DDMONYYYYTHH:MM	×	Preferred Term
	XXX-YYYY	DDMONYYYYTHH:MM	DDMONYYYYTHH:MM	×	Preferred Term

Source: list SAS datasets used to create listing
SAS X.Y

DDMONYYYYTHH:MM
program_name

Pacira Pharmaceuticals
Listing 16.2-6.3: Passive and Active Knee Flexion - Randomized Subjects
Treatment: TTTTTT

Protocol: 404-C-201

Site	Subject	Timepoint [1]	Time of Assesment [2]	Date and Time	Passive Knee Flexion (Degrees)	Active Knee Flexion (Degrees)
XXX	XXX-YYYY	Baseline	N/A	DDMONYYYYTHH:MM	XXX	XXX
		Day 1	N/A	DDMONYYYYTHH:MM	XXX	XXX
		Day 2	N/A	DDMONYYYYTHH:MM	XXX	XXX
		Day 3	N/A	DDMONYYYYTHH:MM	XXX	XXX
XXX	XXX-YYYY	Baseline	AM	DDMONYYYYTHH:MM	XXX	XXX
		Day 1	AM	DDMONYYYYTHH:MM	XXX	XXX
		Day 1	PM	DDMONYYYYTHH:MM	XXX	XXX
		Day 2	AM	DDMONYYYYTHH:MM	XXX	XXX
		Day 2	PM	DDMONYYYYTHH:MM	XXX	XXX
		Day 3	AM	DDMONYYYYTHH:MM	XXX	XXX
. . .						

[1] Timepoints are Day 1 through Day 3 prior to Protocol Amendment 2 and Day 1 through Day 5 after Protocol Amendment 2.

[2] AM/PM is collected only after Amendment 2.

Source: list SAS datasets used to create listing
SAS X.Y

DDMONYYYYTHH:MM
program_name

Pacira Pharmaceuticals (Page X of Y)
Listing 16.2-6.4: TUG Test - Randomized Subjects
Treatment: TTTTTT

Site	Subject	Timepoint[1]	Date and Time	Done?	Reason not done	Duration of Test (seconds)	Aid Used?	Physical Assistance
XXX- XXX	YYYY	Baseline	DDMONYYYYTHH:MM	Y		XXX	XXX	X
		Day 1	DDMONYYYYTHH:MM	N	XXXXXXXXXXXXXXXXXX	XXX	XXX	X
		Day 2-AM	DDMONYYYYTHH:MM	Y		XXX	XXX	X
		Day 2-PM	DDMONYYYYTHH:MM	Y		XXX	XXX	X
		Unscheduled	DDMONYYYYTHH:MM	Y		XXX	XXX	X
		Unscheduled	DDMONYYYYTHH:MM	Y		XXX	XXX	X
		Day 7	DDMONYYYYTHH:MM	Y		XXX	XXX	X

Physical Assistance: 1=Total Assistance 2=Maximal Assistance 3=Moderate Assistance
4=Minimal Assistance 5=Supervision 6=Modified Independence 7=Complete Independence
[1] Hospital Discharge only applies to the subjects enrolled after Protocol Amendment 2.

Source: list SAS datasets used to create listing
SAS X.Y

DDMONYYYYTHH:MM
program_name

Pacira Pharmaceuticals
Listing 16.2-6.5: Numeric Rating Scale (NRS) - Randomized Subjects
TREATMENT: *treatment-name*

Protocol: 404-C-201

Site	Subject	Timepoint	Date	Time From Dose			NRS Score	NRS-R	Performed?
				Scheduled (hr)	Actual (hr)	Deviation (hrs)			
XXX	XXX-YYYY	D1	Preop	DDMONYYYYTHH:MM	XX.XX	XX.XX	XXXX	XX.X	Y
		PACU		DDMONYYYYTHH:MM	XX.XX	XX.XX	XXXX	XX.X	Y
		2h		DDMONYYYYTHH:MM	XX.XX	XX.XX	XXXX	XX.X	Y
		4h		DDMONYYYYTHH:MM	XX.XX	XX.XX	XXXX	XX.X	Y
		6h		DDMONYYYYTHH:MM	XX.XX	XX.XX	XXXX	XX.X	Y
		8h		DDMONYYYYTHH:MM	XX.XX	XX.XX	XXXX	XX.X	Y
		12h		DDMONYYYYTHH:MM	XX.XX	XX.XX	XXXX	XX.X	Y
		16h		DDMONYYYYTHH:MM	XX.XX	XX.XX	XXXX	XX.X	Y
		24h		DDMONYYYYTHH:MM	XX.XX	XX.XX	XXXX	XX.X	Y
		36h		DDMONYYYYTHH:MM	XX.XX	XX.XX	XXXX	XX.X	Y
		48h		DDMONYYYYTHH:MM	XX.XX	XX.XX	XXXX	XX.X	Y
		72h		DDMONYYYYTHH:MM	XX.XX	XX.XX	XXXX	XX.X	Y
		Day 7		DDMONYYYYTHH:MM	XX.XX	XX.XX	XXXX	XX.X	Y

NRS: 0=No pain to 10=Worst Pain Imaginable

ND=Not Done NA=Not Applicable

* = out of window

Source: list SAS datasets used to create listing

SAS X.Y

DDMONYYYYTHH:MM

program_name

Pacira Pharmaceuticals (Page X of Y) Protocol: 404-C-201
Listing 16.2-6.6: Knee and Thigh Circumference Measurements - Randomized Subjects

TREATMENT: *treatment-name*

Site	Subject	Timepoint	Date Time	Thigh (cm)		Knee (cm)		Procedure Name
				Right	Left	Right	Left	
XXX	XXX-YYYY	D1 Preop	DDMONYYYYTHH:MM	XX.X	XX.X	XX.X	XX.X	Right TKA
		48h	DDMONYYYYTHH:MM	XX.X	XX.X	XX.X	XX.X	Right TKA
		Day7	DDMONYYYYTHH:MM	XX.X	XX.X	XX.X	XX.X	Right TKA
XXX	XXX-YYYY	D1 Preop	DDMONYYYYTHH:MM	XX.X	XX.X	XX.X	XX.X	Left TKA
		48h	DDMONYYYYTHH:MM	XX.X	XX.X	XX.X	XX.X	Left TKA
		Day7	DDMONYYYYTHH:MM	XX.X	XX.X	XX.X	XX.X	Left TKA
XXX	XXX-YYYY	D1 Preop	DDMONYYYYTHH:MM	XX.X	XX.X	XX.X	XX.X	Right TKA
		48h	DDMONYYYYTHH:MM	XX.X	XX.X	XX.X	XX.X	Right TKA
		Day7	DDMONYYYYTHH:MM	XX.X	XX.X	XX.X	XX.X	Right TKA

ND=Not Done, NA=Not Applicable

* = out of window

Source: list SAS datasets used to create listing
SAS X.Y

DDMONYYYYTHH:MM
program_name

Pacira Pharmaceuticals
Listing 16.2-6.7: Surgical Wound Aspect Score (SWAS) - Randomized Subjects
TREATMENT: *treatment-name*

Site	Subject	Timepoint	Date Time	Numerical Score			
				Wound	Oozing	Erythema	Ecchymosis
XXX	XXX-YYYY	D1 Preop	DDMONYYYYTHH:MM	x		x	x
		48h	DDMONYYYYTHH:MM	x		x	x
		Day7	DDMONYYYYTHH:MM	x		x	x
XXX	XXX-YYYY	D1 Preop	DDMONYYYYTHH:MM	x		x	x
		48h	DDMONYYYYTHH:MM	x		x	x
		Day7	DDMONYYYYTHH:MM	x		x	x
XXX	XXX-YYYY	D1 Preop	DDMONYYYYTHH:MM	x		x	x
		48h	DDMONYYYYTHH:MM	x		x	x
		Day7	DDMONYYYYTHH:MM	x		x	x

ND=Not Done, NA=Not Applicable,

* = out of window

Source: list SAS datasets used to create listing
SAS X.Y

DDMONYYYYTHH:MM
program_name

Pacira Pharmaceuticals
Listing 16.2-7: Phone Calls - Randomized Subjects

Protocol: 404-C-201

Treatment: TTTTTT

Site	Subject	Date of Phone Contact	Scheduled Timepoint	Was the Call Made?	Was there a reoperation?	Number of Reoperations	Independent Ambulation?	Date of Ind. Amb.
XXX	XXX-YYYY	DDMONYYYY	Day 14	Y	N	NA	N	NA
	XXX-YYYY	DDMONYYYY	Day 30	Y	N	NA	Y	DDMONYYYY
	XXX-YYYY	DDMONYYYY	Day 60	Y	N	NA	Y	DDMONYYYY
XXX	XXX-YYYY	DDMONYYYY	Day 14	N	ND	NA	ND	NA
	XXX-YYYY	DDMONYYYY	Day 30	Y	N	NA	N	NA
	XXX-YYYY	DDMONYYYY	Day 60	Y	N	NA	Y	DDMONYYYY
XXX	XXX-YYYY	DDMONYYYY	Day 14	Y	N	NA	N	NA
	XXX-YYYY	DDMONYYYY	Day 30	Y	N	NA	N	NA
	XXX-YYYY	DDMONYYYY	Day 60	Y	Y	x	N	NA

ND=Not Done, NA=Not Applicable

Source: list SAS datasets used to create listing
SAS X.Y

DDMONYYYYTHH:MM
program_name

Pacira Pharmaceuticals
Listing 16.2-8: Neurological Assessment - Randomized Subjects

Protocol: 404-C-201

Treatment: TTTTTTT

Site	Subject	Date and Time Of Assessment	Time From Dose			Questions					
			Scheduled (hr)	Actual (hr)	Deviation (mins)	1	2	3	4	5	6
XXX	XXX-YYYY	DDMONYYYYTHH:MM	Screening	NA	NA	XXX	XXX	XXX	XXX	XXX	XXX
		DDMONYYYYTHH:MM	D1 PREOP	NA	NA	XXX	XXX	XXX	XXX	XXX	XXX
		DDMONYYYYTHH:MM	12	0.XX	X	XXX	XXX	XXX	XXX	XXX	XXX
		DDMONYYYYTHH:MM	24	X	X	XXX	XXX	XXX	XXX	XXX	XXX
		DDMONYYYYTHH:MM	36	ND							
		DDMONYYYYTHH:MM	48	X	X	XXX	XXX	XXX	XXX	XXX	XXX
		DDMONYYYYTHH:MM	60	X	X	XXX	XXX	XXX	XXX	XXX	XXX
		DDMONYYYYTHH:MM	72	XX	X	XXX	XXX	XXX	XXX	XXX	XXX
		DDMONYYYYTHH:MM	96	XX	X	XXX	XXX	XXX	XXX	XXX	XXX
		DDMONYYYYTHH:MM	Screening	NA	NA	XXX	XXX	XXX	XXX	XXX	XXX
XXX-YYYY	XXX-YYYY	DDMONYYYYTHH:MM	D1 PREOP	NA	NA	XXX	XXX	XXX	XXX	XXX	XXX
		DDMONYYYYTHH:MM	12	XX	X	XXX	XXX	XXX	XXX	XXX	XXX
		DDMONYYYYTHH:MM	24	XX	X	XXX	XXX	XXX	XXX	XXX	XXX
		DDMONYYYYTHH:MM	36	XX	-X	XXX	XXX	XXX	XXX	XXX	XXX
		DDMONYYYYTHH:MM	48	XX	X	XXX	XXX	XXX	XXX	XXX	XXX
		DDMONYYYYTHH:MM	60	XX	X	XXX	XXX	XXX	XXX	XXX	XXX
		DDMONYYYYTHH:MM	72	XX	X	XXX	XXX	XXX	XXX	XXX	XXX
		DDMONYYYYTHH:MM	96	XX	X	XXX	XXX	XXX	XXX	XXX	XXX

- 1) Is subject oriented?
- 2) Do you have numbness of the lips, the tongue or around the mouth?
- 3) Do you have a metallic taste in your mouth?
- 4) Are you having problems with your hearing not related to the use of a hearing aid?
- 5) Are you having problems with your vision no related to the use of eye glasses?
- 6) Are your muscles twitching?

Source: list SAS datasets used to create listing
SAS X.Y

DDMONYYYYTHH:MM
program_name

Pacira Pharmaceuticals
(Page X of Y)
Listing 16.2-9: Electrocardiogram Findings - Investigator Assessment - All Subjects
Treatment: DepoTXA 400

Protocol: 404-C-201

Site	Subject	Date and Time of Sample	Time From Dose				If "Abnormal", specify
			Scheduled Timepoint	Actual (hr)	Deviation (mins)	Finding	
XXX	XXX-YYYY	DDMONYYYYTHH:MM	D1PreOp	NA	NA	Normal	
		DDMONYYYYTHH:MM	1h	XX.X	X	Normal	
		DDMONYYYYTHH:MM	12h	XX.X	X	Normal	
	XXX-YYYY	DDMONYYYYTHH:MM	D1PreOp	NA	NA	Normal	
		DDMONYYYYTHH:MM	1h	XX.X	X	Normal	
		DDMONYYYYTHH:MM	12h	XX.X	X	Normal	
	XXX-YYYY	DDMONYYYYTHH:MM	D1PreOp	NA	NA	Normal	
		DDMONYYYYTHH:MM	1h	XX.X	X	Normal	
		DDMONYYYYTHH:MM	12h	XX.X	X	Normal	

NA=Not applicable

ND=Not done

Source: list SAS datasets used to create listing
SAS X.Y

DDMONYYYYTHH:MM
program_name

Pacira Pharmaceuticals
Listing 16.2-10: Vital Signs - All Subjects
Treatment: TTTTTTT
SITE: XXX

(Page X of Y)

Protocol: 404-C-201

Subject	Visit	Date and Time	Time from Dose			Heart Rate (bpm)	Blood Pressure		Body Mass		
			Sched (hr)	Actual (hr)	Deviation (mins)		Sys. (mmHg)	Dia. (mmHg)	Height (cm)	Weight (kg)	Index (m/kg ²)
XXX-YYYY	Screening	DDMONYYYYTHH:MM	NA	NA	NA	XX	XXX	XXX	XXX	XXX	XXX
	D1 Preop	DDMONYYYYTHH:MM	0	X	X	XX	XXX	XXX			
	5 min	DDMONYYYYTHH:MM	0.08	X	X	XX	XXX	XXX			
	15 min	DDMONYYYYTHH:MM	0.25	X	X	XX	XXX	XXX			
	30 min	DDMONYYYYTHH:MM	0.50	X	-X	XX	XXX	XXX			
	1h	DDMONYYYYTHH:MM	1	X	X	XX	XXX	XXX			
	2h	DDMONYYYYTHH:MM	2	X	X	XX	XXX	XXX			
	4h	DDMONYYYYTHH:MM	4	X	X	XX	XXX	XXX			
	6h	DDMONYYYYTHH:MM	6	X	X	XX	XXX	XXX			
	8h	DDMONYYYYTHH:MM	8	X	X	XX	XXX	XXX			
	12h	DDMONYYYYTHH:MM	12	X	X	XX	XXX	XXX			
	16h	DDMONYYYYTHH:MM	16	X	X	XX	XXX	XXX			
	24h	DDMONYYYYTHH:MM	24	X	X	XX	XXX	XXX			
	36h	DDMONYYYYTHH:MM	36	X	X	XX	XXX	XXX			
	48h	DDMONYYYYTHH:MM	48	X	X	XX	XXX	XXX			
	60h	DDMONYYYYTHH:MM	60	X	X	XX	XXX	XXX			
	72h	DDMONYYYYTHH:MM	72	X	X	XX	XXX	XXX			
	96h	DDMONYYYYTHH:MM	96	X	X	XX	XXX	XXX			

Source: list SAS datasets used to create listing
SAS X.Y

DDMONYYYYTHH:MM
program_name

Pacira Pharmaceuticals
Listing 16.2-11.1: All Adverse Events - All Subjects

(Page X of Y)

Protocol: 404-C-201

Treatment: TTTTTT

Site	Subject	TEAE	Data Type	Data
XXX	XXX-YYYY	N	Start	DDMONYYYYTHH:MM
			Stop	DDMONYYYYTHH:MM
			AE Number	X
			System Organ Class	XXXXXXXXXXXXXXXXXXXX
			Preferred	XXXXXXXXXXXXXXXXXXXX
			Verbatim	XXXXXXXXXXXXXXXXXXXX
			Severity	XXXXXXX
			Relationship to Study Drug	XXXXXXX
			Action Taken	XXXXXXXXXXXXXXXXXXXX
			Outcome	XXXXXXXXXXXXXXXXXXXX
			Serious	XXX
			Serious Cause(s)	XXXXXXXXXXXXXX
				XXXXXXXXXXXXXXXXXXXX

TEAE: Treatment-emergent AE (Y=TEAE/N=Not TEAE)

Source: list SAS datasets used to create listing
SAS X.Y

DDMONYYYYTHH:MM
program_name

Note to programmer: If AE is ongoing, put ONGOING in stop row. Do not split an AE across pages. Insert a page break between subjects. This this template for the following listings:

Listing 16.2-11.2.1: Treatment-Emergent Adverse Events - Randomized Subjects

Listing 16.2-11.2.2: Treatment-Emergent Study Drug Related Adverse Events - Randomized Subjects

Listing 16.2-11.3: All Serious Adverse Events - All Subjects

Listing 16.2-11.3.CT: All Non-Serious Adverse Events - All Subjects

Listing 16.2-11.4.1: Treatment-Emergent Serious Adverse Events - Randomized Subjects

Listing 16.2-11.4.1.CT: Treatment-Emergent Non-Serious Adverse Events - Randomized Subjects

Listing 16.2-11.4.2: Treatment-Emergent Study Drug Related Serious Adverse Events - Randomized Subjects

Pacira Pharmaceuticals
Listing 16.2-12.1: All Prior Medications - Randomized Subjects
Treatment: TTTTTT

Protocol: 404-C-201

Site	Subject	Category	Data Type	Data
XXX	XXX-YYYY		Start	DDMONYYYYTHH:MM
			Stop	DDMONYYYYTHH:MM
			Medication Number	X
			ATC Level 1	XXXXXXXXXXXXXXXXXXXX
			ATC Level 2	XXXXXXXXXXXXXXXXXXXX
			ATC Level 3	XXXXXXXXXXXXXXXXXXXX
			ATC Level 4	XXXXXXXXXXXXXXXXXXXX
			Preferred Name	XXXXXXXXXXXXXXXXXXXX
			Verbatim	XXXXXXXXXXXXXXXXXXXX
			Route	XXXXXXX
